## **RESEARCH PROTOCOL**

This study is a pre-post exercise and diet intervention study with 2 groups: firefighters and civilians. For the study, firefighters will be recruited from local fire departments and civilians will be recruited from the surrounding areas. The only compensation will be for parking while they are on campus for testing appointments. A study description document is attached which will be used to supplement the word-of-mouth advertising done by walking into local firehouses.

The population is seemingly healthy and low-risk, so physician referral or approval is not needed. Criteria for inclusion: adult 18 years of age and older; no history of renal disease, diabetes, or cardiovascular incident requiring surgery; no existing orthopedic issues that preclude exercise; no more than one anti-hypertensive or cholesterol medication.

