#### 4. At-home and self-report 6-week intervention (circuit workout 3-times per week and a Mediterranean diet)

Each participant will undergo 6-weeks of intervention (diet and exercise). They will self-report the number of times per week that they complete the circuit workout, and they will self-report the number of servings per food group that they eat while following the diet. The workouts are done at home, in the fire station, or in a fitness center.

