#### **Diet Intervention:**

The Mediterranean diet includes a high consumption of fruits and vegetables, a moderate consumption of fish, nuts, and wine, and a low consumption of red meat and other meat products. Also, olive oil is the principal source of fat instead of other types of oils. We teach them these basics and the manual has many examples.

During the study, all participants will receive the diet information, will have online access to diet information by our website, <http://www.theheartlab.org/#dietexercise>, will receive weekly educational documents and tips through email, will be provided with informational websites, and receive many lessons on serving size. We also provide all participants with sample serving size containers to get them started.

For the duration of the diet intervention, they will be asked to track their diet and enter serving numbers into our research website each week. The manual and the website have a nice checklist that can be used to track their weekly diet.

Also, the **study** manual and website have been used for the prior cohorts of data collection for this study.

Here is a quick summary of the number of servings per week they will target and track during each week of the diet intervention (some serving numbers may be reduced based on body size though):

Vegetables = more than 28 per week  
Low/Non-Fat Dairy = 14-21 per week  
Fish = more than 4 per week  
Red Meat = less than 2 per week  
Nuts/Healthy Oils = less than 8 per week  
Sweets/Processed Food = less than 4 per week

Fruits = more than 21 per week  
Grains/Potatoes = 42-49 per week  
Poultry = less than 3 per week  
Beans = more than 3 per week  
Other Fats/Oils = less than 8 per week

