## **6-Week Intervention: Exercise Training Component**

The exercise intervention will be self-report. This means that the exercises will be done at home or in the fire house or in a fitness center. All participants are asked to complete the circuit workout 3 times per week for the 6-week period. For the workout, each station below will be done 3 times within each workout, and it should take around 45 minutes. The workout can be done by going through each station and rotate back around 3 times, or the workout can be done by doing each station 3 times and moving on to the next station. Either way that they choose to complete the workout, the amount of work that they will do is the same, so it gives flexibility to pick each time.

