## **Post-Intervention Testing Visits**

They will complete the exact same tests after the intervention as they did before.

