## RISKS

The possible **risks**, exactly as described in the consent form, include the following:

*Loss of Confidentiality:* Once others know that you are participating in the study, you may lose some confidentiality. Fire crews work in close quarters and some spend time living together in the fire house, so confidentiality may be lost by your presence at the testing appointments. We will reduce this risk because your name will not be on any documents and your personal data will not be shown to anyone during the test sessions.

*Depression, Anxiety, and Stress Scales (DASS-21):* The risk associated with completing this short 21-item survey is that you may feel uncomfortable while answering the questions. If you feel this and your symptoms are severe, we will work with you to refer you to a proper clinician who is part of your health network.

*Blood glucose, cholesterol, and blood draw:* These measurements will involve a finger prick and a needle stick. The risks associated are slight discomfort in the site. These are routine and conventional procedures used to measure blood levels of metabolites. Minor risks include a small amount of bleeding under the skin (bruising), but this has been reported in <10% of the cases, dizziness, and a very small risk of infection (1 in 1000). The risk of infection will be reduced by proper cleaning and antiseptic techniques by the technician.

*Blood vessel studies:* The blood vessel ultrasound studies may include discomfort in the arm and leg when the cuff squeezes to take a measurement. This feeling could be similar to what is felt when a foot or leg falls asleep after sitting in certain positions. This is not a risk to your health, but it is a discomfort. To help with this risk, we recommend that you stay very still and as the blood flows back to the arm and the feeling will go away.

*Fitness testing/training:* The risk of any exercise is injury to muscles, joints, ligaments, and tendons. It has been found that in 1 out of every 70,000 exercise tests, a person could die from heart problems. In medical terms, doctors call this a rare event. Because you are otherwise healthy with no known risk factors, the risks of a medical problem are even lower. You are aware that if any exercise makes you uncomfortable, you should notify us immediately.

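### Harms from a mostly off-site exercise and diet programme reach the study team only if participants volunteer them, and the plan describes no scheduled harm question, harm record or harms summary

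*Combined protocol and SAP*

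**What the plan says.** **Risks and how they are reported.** The fitness testing/training paragraph of RISKS names musculoskeletal injury and a rare risk of cardiac death, the latter put at 1 in 70,000 exercise tests. It then says: "You are aware that if any exercise makes you uncomfortable, you should notify us immediately". The diet paragraph of RISKS likewise asks participants to tell lab staff if a problem arises.

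**The training.** Under the Exercise Training Component, "All participants are asked to complete the circuit workout 3 times per week for the 6-week period", and of each workout the plan says "it should take around 45 minutes". Step 4 of the Brief protocol summary adds: "The workouts are done at home, in the fire station, or in a fitness center".

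**What participants report.** Step 4 says "They will self-report the number of times per week that they complete the circuit workout". Diet Intervention says "they will be asked to track their diet and enter serving numbers into our research website each week".

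**Checks at visits.** Orthopaedic status appears as an entry criterion under RESEARCH PROTOCOL: "no existing orthopedic issues that preclude exercise". Step 5 of the Brief protocol summary says that at each lab visit the day's measures are explained, questions are invited and consent is asked again. Post-Intervention Testing Visits says: "They will complete the exact same tests after the intervention as they did before".

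**Analysis.** DATA lists repeated measures ANOVA, paired and independent t-tests, correlation and regression. It does not mention harms.

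**The concern.** The plan names specific risks of the programme but describes no scheduled question about them, no place to record them and no table to report them in. Two things are at stake.

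**Interpretation of safety.** BENEFITS says that a simple diet and exercise programme that lowers the pager surge could save lives. A reader will want to set any such benefit against the harms. If harms are known only when volunteered, a report of none could mean that none occurred or that nobody asked.

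**The fitness comparisons in aim 2.** Someone hurt in training may skip a post-test or perform it impaired. A skipped test removes that person from the paired comparison; an impaired test stays in with a lower score. Without a recorded reason, neither can be recognised or described when the results are read.

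**Working it through.** The plan states no figure for the share of supervised exercise or for expected harms, so there is none to reproduce. The check is a count and a comparison of sections.

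**Inputs**
- Workouts: 3 per week for 6 weeks, about 45 minutes each (Exercise Training Component).
- Staff-run exercise sessions: one fitness test before and one after, about 45 minutes each (Fitness Testing Appointment; Brief protocol summary, steps 3 and 5).
- Adherence: not given, so varied below as an assumption.

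**Share of planned exercise that is off site**
- Sessions: 3 × 6 = 18 off site and 2 staff-run, so 18 / (18 + 2) = 18/20 = 90%.
- Time: 18 × 45 = 810 minutes off site and 2 × 45 = 90 minutes staff-run, so 810/900 = 90%.

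**If fewer workouts are done**, with adherence *a*, the share is 18*a* / (18*a* + 2):

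| Assumed adherence | Off-site workouts | Share off site |
|---|---|---|
| 100% | 18 | 90.0% |
| 90% | 16.2 | 89.0% |
| 75% | 13.5 | 87.1% |
| 50% | 9 | 81.8% |
| 25% | 4.5 | 69.2% |

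The share stays above 80% down to half adherence. The 1 in 70,000 figure is per exercise test, so it describes the 2 test sessions and not the 18 workouts.

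**Where a harm could be captured**

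| Contact point | Content described | Harm question stated? |
|---|---|---|
| Weekly exercise report | Number of workouts | No |
| Weekly diet report | Servings | No |
| Each lab visit | Explanation, questions, renewed consent | No |
| Participant contacts staff | Discomfort, or a problem with the diet | Participant-initiated only |
| Analysis in DATA | Comparisons and correlations | No summary |

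In the available text the number of scheduled harm questions between pre- and post-testing is zero.

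**Post-testing.** Fitness Testing Appointment describes three kinds of test held to exhaustion or until position or balance fails: plank, single-leg stand and wall sit. The treadmill test is submaximal. A paired t-test uses only people with both values, so a test not done drops the pair and an impaired test keeps it. The plan does not say that the reason is recorded in either case.

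**The case against.** **Absence is hard to prove here.** One passage between Post-Intervention Testing Visits and DATA was not available, and the web form, study manual and questionnaires are not reproduced. The sections on self-report say what participants enter without claiming to list every field, and the sentence on notifying staff is consent wording, not a monitoring plan. This stands, and it limits the point to the available text.

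A reader might also infer several stronger things that the documents do not support.

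- *That harms will go uncounted, or that volunteering misses most injuries.* A harm that is called in would reach staff, and the documents give no rate of under-reporting. Only *may miss* is justified.
- *That 90% of sessions lack a harm question and the rest have one.* The 90% is the planned off-site share. The available text shows no harm question at any session, including the two tests. Nor is 90% a measure of risk. That the workouts are unsupervised is itself an inference from location and self-report.
- *That injured people must perform the exhaustion tests.* The sentence on repeating the tests describes the battery. Participants are asked again for consent, the holds also end on loss of position or balance, and a participant could decline.
- *That lower scores after injury are a bias to be removed.* A score reduced by a training injury is arguably part of the programme's effect. Withholding tests from injured people would take them out of the paired comparisons and could flatter the programme. It would also be a clinical rule.
- *That the adherence results or the surge comparison in aim 1 are distorted.* DATA states no adherence analysis, and no effect on the surge comparison has been shown.

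**Conclusion.** The point holds in a limited form. On the available text, harms are learned of only when a participant volunteers them, while 90% of planned exercise sessions (18 of 20) take place off site with no staff presence described. That share assumes full adherence; it would be 81.8% at half adherence.

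The size of any under-reporting cannot be estimated from the documents, and the conclusion does not need it: with no scheduled question and no stated record or summary, a report of no harms could not be interpreted. The effect on the analysis is confined to post-tests missed or impaired by injury with no recorded reason, chiefly the fitness measures in aim 2.

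The conclusion rests on the unavailable passage and the web form not already containing a harm item. If they do, what remains is to state it in the protocol and add the reporting. The change is worth making because it is cheap and cannot be recovered once the six weeks are over.

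**What to change.** 1. **Weekly self-report** (Brief protocol summary, step 4; Diet Intervention): add one required item asking about any injury, chest symptom or food reaction that week, and the number of workouts missed because of it. Have existing study personnel review the answers weekly.
2. **Post-intervention lab visits** (Brief protocol summary, step 5): ask the same question alongside the renewed consent check.
3. **Post-Intervention Testing Visits:** record which tests were not done or were stopped early, and why.
4. **DATA:** report harm counts by group (firefighters and civilians) and the number of post-tests affected, beside the main results.

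How an injured participant is handled at post-testing is for the investigators to settle. They should reconcile the entry criterion in RESEARCH PROTOCOL, the visit check in step 5 and the statement that the tests are repeated unchanged. No clinical rule is proposed here.

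**Cost:** one web-form item, one question at existing visits, a short table, and a little participant and staff time. No new visit or staff post is needed.

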## BENEFITS

The possible **benefits**, exactly as described in the consent form, include the following:

By participating in this study it is hoped that you will gain information about your health and fitness levels. You also get to participate in a lifestyle intervention and find how the intervention changes your health. Whether these benefits will occur for you cannot be guaranteed.

Also the broader benefit to the community is great by your participation. Firefighters across the world need to be aware of their blood pressure levels and should know that the blood pressure surge can be large with pager alarm. If this research can identify potential relationships between the blood pressure surge and cardiovascular health, the knowledge could save lives. Also, if this study can show that a simple diet and exercise program can reduce the blood pressure surge, we could save lives.

